#### **5.4.2.6 Intracranial, Extracranial and Overall Disease Control Rate at 16 Weeks – RECIST**

Intracranial, extracranial, and overall disease control rates (DCR) are defined as the proportion of patients with a CR or PR (based on two consecutive assessments  $\geq 4$  weeks apart) or stable disease (SD) at 16 weeks from study treatment initiation, as determined by the investigator according to RECIST v1.1. The denominator is all patients in the evaluable population.

Week 16 occurs at Study Day 112. Allowing 7 days after the exact Week 16, assessments that occur between Study Day 112 and Study Day 119 (inclusive) will be considered as a Week 16 assessment.

Patients with a CR or PR or SD at 16 weeks from study treatment initiation are patients:

- With a CR or PR assessed within the window of Study Days 112-119 inclusive and followed by a consecutive CR or PR assessment in the next  $\geq 4$  weeks.

OR

- With a CR or PR assessed prior to the Study Day 112 and followed by a consecutive CR or PR assessment in the next  $\geq 4$  weeks and on or after Study Day 112.

OR

- With a SD assessed within the window of Study Days 112-119 inclusive.

DCR will be presented together with a 95% Pearson-Clopper CI.

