3.3.3 Rationale for Patient Populations

Brain metastases represent a significant therapeutic challenge and are particularly common in advanced melanoma (see Section 1.1). Immunotherapy and MAPK targeted treatments have shown promise in the treatment of advanced melanoma including in patients with CNS disease (see Sections 1.1 and 1.3.2) and are being studied in combination in large, randomized Phase III studies that unfortunately exclude most patients with CNS disease (see Section 1.3.2.4). Study MO39136 will enrol patients with CNS disease that may otherwise be excluded from research into this dual-pronged treatment approach that has the potential to be of benefit in this hard-to-treat population.

$\text{BRAF}^{\text{V600}}$ status must be known prior to study enrollment in order to determine appropriate treatment cohort assignment. Patients with $\text{BRAF}^{\text{V600}}$ mutation-positive disease will be assigned to Cohort 2 wherein treatment includes the BRAF inhibitor vemurafenib that abrogates constitutive MAPK activation due to $\text{BRAF}^{\text{V600}}$ mutation. Patients whose disease does not harbour a $\text{BRAF}^{\text{V600}}$ mutation will be assigned to treatment in Cohort 1.

All patients must have measurable CNS disease to enable assessment of the primary study endpoint, intracranial ORR. Though consistent with RECIST v1.1, the criteria for CNS disease measurability have been adapted as in other trials of CNS melanoma metastases to ensure CNS lesions can be accurately assessed (Tawbi et al. 2017).

To enable inclusion of patients who have few other treatment options, prior systemic treatment for advanced disease and local treatments for brain metastases, with the exception of treatments that may directly affect the experimental regimens in this study or assessment of efficacy, are allowed. Additional study eligibility criteria have been established to ensure adequate health to undergo experimental therapy and ensure the absence of potential contraindications to the study regimens.

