#### 4. ANALYSIS SETS

The following populations are defined:

Population	Definition
Safety-evaluable Population	All participants received at least one dose of study treatment (e.g., atezolizumab, cobimetinib, or vemurafenib)
Evaluable Population	All enrolled patients who received study medication and have at least two post-baseline intracranial tumour assessments for response evaluation
PRO-evaluable Population	All patients who received any amount of any study medication (e.g., atezolizumab, cobimetinib, or vemurafenib) and have a baseline and at least one post baseline PRO assessment in the questionnaire of interest (EORTC QLQ-C30 or EORTC QLQ-BN20)

EORTC QLQ-C30 and QLQ-BN20=European Organization for Research and Treatment of Cancer Quality of Life questionnaire core questionnaire and brain cancer specific module; PRO=patient-reported outcome.

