## **5. STATISTICAL ANALYSES**

### **5.1 GENERAL CONSIDERATION**

A primary study analysis that includes analyses of all efficacy endpoints and safety summaries will be conducted based on data collected up to 6 months after the last patient is enrolled in the study (last patient in [LPI]). The final study analysis including updated analyses of safety and efficacy endpoints will be conducted based on data collected up to 24 months after LPI.

Unless otherwise indicated, efficacy analyses will be based upon the Evaluable population in each cohort consisting of all enrolled patients who received study medication and have at least two post-baseline tumour assessments for response evaluation. Analyses of safety, survival, corticosteroid use, and time to subsequent intracranial or systemic anti-cancer treatment endpoints will be conducted based upon the Safety evaluable population in each cohort consisting of all patients who received at least one dose of study medication. Analyses of patient-reported outcome (PRO) endpoints will be conducted based upon the PRO-evaluable population.

Any incomplete or missing death date will be handled separately for safety and efficacy analyses. In safety analyses, all deaths will be included, regardless of completeness of death date; patients who died with a partial or missing death date will be included as an event. In efficacy analyses, a death is considered an event only if a complete death date is available; patients who died with only a partial or missing death date will not be considered as a death event.

Based on the results of the primary analysis for Study CO39722 (IMspire170) of cobimetinib plus atezolizumab combination in previously untreated advanced BRAFV600 wild-type melanoma patients (see Section 1.3.2.4 of the study protocol), enrollment in the BRAFV600 wild-type cohort was discontinued. The primary endpoint will not be evaluated on Cohort 1. Only a subset of analysis on efficacy secondary endpoints will be performed.

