#### **5.3.4.1 Subgroup Analyses for Primary Endpoint**

The consistency of the primary efficacy results will be examined in subgroups defined by demographic characteristics and clinical and biological prognostic factors. Summaries of intracranial ORR, including 95% Pearson-Clopper CIs, will be produced for each of the defined subgroups, and displayed in a Forest plot ([Lewis and Clarke 2001](#)).

The subgroups to be considered include, but may not be limited to, the following:

- Age ( $\leq 65$  years,  $>65$  years)
- Race (non-White, White)
- Sex (female, male)
- Eastern Cooperative Oncology Group (ECOG) performance status (0, 1)
- programmed death ligand 1 (PD-L1) status
- Lactic Acid Dehydrogenase (LDH) ( $\leq$  upper limit of normal [ULN],  $>ULN$ )

- BRAF mutation subtype (V600E, V600K)
- Extracranial sum of longest diameter
- Number of target lesion (intracranial, extracranial)
- Receiving prior steroid therapy
- Organ involvement (site of target lesion): patients with brain lesion(s) only, patients with brain lesion(s) and other lesions.

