## **5.4 SECONDARY ENDPOINTS ANALYSES**

Unless otherwise noted, all efficacy analyses will be performed on both the evaluable patient population and all treated patients (safety population).

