#### **5.4.2.2 Extracranial Objective Response Rate – RECIST**

Extracranial ORR is defined as the proportion of patients with either a CR or PR in their extracranial disease based on two consecutive assessments  $\geq 4$  weeks apart, as determined by the investigator according to RECIST v1.1.

The extracranial ORR will be presented together with a 95% Pearson-Clopper CI.

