### **5.5.1.2 Intracranial, Extracranial and Overall Objective Response Rate – Immune-Modified RECIST**

ORR in intracranial, extracranial and overall disease are defined as described in Sections [5.4.2.1](#), [5.4.2.2](#), and [5.4.2.3](#) but determined by investigator according to immune-modified RECIST with modified measurability definition for intracranial lesions ( $\geq 0.5$  cm by MRI) and allowing up to five intracranial target lesions.

Intracranial, extracranial, and overall ORR will be analyzed using the same methods as described in Section [5.3.2](#).

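### Extracranial DCR is divided by all evaluable patients, including any with no extracranial disease, whose coding is left undefined; extracranial ORR takes the same denominator by default

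*SAP*

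**What the plan says.** SAP 5.4.2.6 defines intracranial, extracranial and overall DCR together and gives all three one denominator: "The denominator is all patients in the evaluable population". A patient is controlled by one of three routes: a confirmed CR or PR assessed in Study Days 112 to 119; a CR or PR before Day 112 that is confirmed on or after Day 112; or SD in Days 112 to 119.

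SAP Section 4 places treated patients in the Evaluable population if they "have at least two post-baseline intracranial tumour assessments for response evaluation". It sets no condition on extracranial disease. Neither does eligibility. Protocol 4.1.1 asks for brain metastases, and Protocol 3.3.3 explains: "All patients must have measurable CNS disease to enable assessment of the primary study endpoint, intracranial ORR".

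For ORR, SAP 5.4.2.2 says: "Extracranial ORR is defined as the proportion of patients with either a CR or PR in their extracranial disease". It names no denominator, so the general rule in SAP 5.1 applies: "Unless otherwise indicated, efficacy analyses will be based upon the Evaluable population in each cohort". SAP 5.4 adds a parallel analysis on the safety population. The immune-modified version in SAP 5.5.1.2 inherits the definition: "ORR in intracranial, extracranial and overall disease are defined as described in Sections" 5.4.2.1 to 5.4.2.3.

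SAP 5.3.4.1 lists this subgroup, for the primary endpoint only: "Organ involvement (site of target lesion): patients with brain lesion(s) only, patients with brain lesion(s) and other lesions".

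**The concern.** Extracranial DCR and ORR are secondary endpoints, and readers will take them as activity against extracranial tumour. A patient with no tumour outside the brain carries no information on that question. Keeping such a patient in the denominator makes the result depend partly on case mix and partly on what the investigator enters for a compartment with nothing in it. Neither is a treatment effect. The confidence interval does not cover either source of error. The all-treated analysis does not help, because the safety population has no extracranial condition either.

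**Working it through.** **1. The plan's own figures.** Cohort 2 plans about 60 patients with 15% drop-out: 60 × (1 − 0.15) = 51, against about 50 stated. At a 50% rate and n=50, 0.50 ± 1.96 × √(0.50 × 0.50/50) = 0.50 ± 0.139, or 36.1% to 63.9%, as in Protocol Table 8 and SAP Table 2. The analyses use Pearson-Clopper limits: 25/50 gives 35.5% to 64.5%, a half-width of 14.5 points.

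**2. Which category can an empty compartment receive?** In Protocol Appendix 5, CR is the disappearance of lesions and PR is a 30% fall in the sum of target diameters. For non-target lesions the categories are CR, Non-CR/Non-PD and PD. The timepoint response table covers only patients with target lesions. None of this describes a compartment without disease. SD, however, is defined residually, as neither enough shrinkage nor enough growth, so an investigator could enter it. Two outcomes are open:

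- No category is assigned: the patient meets none of the three DCR routes and is a failure.
- SD or CR is entered in the Week 16 window: SD counts as disease control at once, CR if confirmed. For ORR, only an entered response such as CR would inflate the rate; SD would leave the patient a non-responder.

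**3. Size.** Let p be the rate among patients with extracranial disease and s the share without it. Both are assumptions; the documents give neither.

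- All such patients counted as failures: reported rate = p(1 − s), shift = −ps.
- All counted as successes: reported rate = p(1 − s) + s, shift = +s(1 − p).

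| True rate p | s = 10% | s = 20% | s = 30% |
|---|---|---|---|
| 40% | 36% or 46% | 32% or 52% | 28% or 58% |
| 50% | 45% or 55% | 40% or 60% | 35% or 65% |
| 60% | 54% or 64% | 48% or 68% | 42% or 72% |

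The first figure in each cell is all failures and the second all successes. The downward shifts are 4, 8 and 12 points; 5, 10 and 15; and 6, 12 and 18. Seven of the nine are below 14.5 points; only 15 and 18 exceed it. The upward shifts, s(1 − p), also span 4 to 18 points. Mixed coding falls between the two.

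**4. Example (invented counts).** Of 50 evaluable patients, 40 have extracranial disease and 20 of those succeed.

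- Denominator as planned, the other 10 as failures: 20/50 = 40.0% (exact 95% CI 26.4 to 54.8). No result above 40/50 = 80% is attainable.
- The other 10 as successes: 30/50 = 60.0%.
- Patients with extracranial disease only: 20/40 = 50.0% (33.8 to 66.2), half-width 16.2 points.

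**5. A neighbouring choice, kept separate.** A patient whose extracranial disease is all non-target can be CR, Non-CR/Non-PD or PD, but not PR or SD. Persistent, non-progressing disease at Week 16 therefore meets none of the three DCR routes. With invented counts of 40 patients with extracranial disease, 22 controlled by the written routes and 2 more Non-CR/Non-PD, the rate is 22/40 = 55.0% (38.5 to 70.7) or 24/40 = 60.0% (43.3 to 75.1).

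**The case against.** Several objections are fair, and they limit what can be claimed.

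- **Direction.** A reader might infer that patients without extracranial disease can only be failures, so that the rates must be understated. The documents do not support that. The coding is undefined and SD is residual, so DCR could move either way.
- **ORR.** A reader might infer that the SAP states a wrong ORR denominator. It states none. Its wording speaks of response in the patient's extracranial disease, which can be read as presupposing such disease. The problem there is a default left unqualified.
- **Are such patients expected?** The brain-only subgroup might be taken as proof. It is defined by site of target lesion, so a patient with only non-target extracranial disease would also fall in it. Eligibility permits patients with no extracranial disease, but nothing says how many to expect.
- **Importance.** The study is descriptive and these are supportive endpoints. In most of the scenarios above the shift is smaller than the sampling half-width. That does not excuse a systematic error, but it keeps the point in proportion.
- **An all-patient rate is legitimate.** So it is, if labelled as such. The SAP does not label it.

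What remains is that the DCR denominator is explicit, includes patients to whom the endpoint does not apply, and comes with no coding rule for them.

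**Conclusion.** The concern holds for extracranial DCR on the explicit text and for extracranial ORR by default, in both planned populations. The reported rates would mix activity with the share of patients who have no extracranial disease and with how their empty compartment is coded. If they receive no category, the understatement is 4 to 18 points at assumed shares of 10% to 30% and true rates of 40% to 60%; if they are entered as SD or CR, the error runs upward. The actual size and direction cannot be fixed from the documents, and if every patient has extracranial disease there is no effect. This should be settled before analysis, but it does not threaten the main result: the primary endpoint, DOR and extracranial PFS need no change.

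**What to change.** Within each planned population (evaluable and all treated):

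1. In SAP 5.4.2.6, and for extracranial ORR in 5.4.2.2 and 5.5.1.2, restrict the denominator to patients with extracranial disease at baseline.
2. Assign no extracranial response category to patients without it.
3. Report the number with no extracranial disease and the number with non-target extracranial disease only.
4. Keep patients who have extracranial disease but no post-baseline extracranial assessment in the denominator, as non-responders or not controlled, so that the restriction does not introduce an opposite bias.

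Two further choices should be decided separately. Counting Non-CR/Non-PD as disease control for non-target-only patients changes the protocol's definition, which allows only CR, PR and SD. If adopted, it should be recorded in SAP Appendix 1 or shown as a sensitivity analysis. Limiting ORR to patients with extracranial target lesions would drop non-target-only patients, who can still reach CR, so it needs its own justification.

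The cost is a three-level baseline flag (extracranial target, non-target only, none) and some SAP wording. Protocol 4.5.6 already requires all measurable and non-measurable lesions to be documented at screening. Precision falls slightly: at a 50% rate the exact half-width goes from about 14.5 to about 16.2 points if n drops from 50 to 40.

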4.5.6 Tumour and Response Evaluations

All measurable and non-measurable lesions must be documented at screening (within 28 days prior to initiation of study treatment). Previously irradiated lesions should not be

Cobimetinib, atezolizumab, vemurafenib — F. Hoffmann-La Roche Ltd

74 / Protocol MO39136, Version 5.0

selected as measurable (target) lesions. Tumour assessments performed as standard of care prior to obtaining informed consent and within 28 days prior to initiation of study treatment do not have to be repeated at screening. All measurable and evaluable lesions should be re-assessed at each subsequent tumour evaluation. Intracranial and extracranial tumour assessments after end of Cycle 2 should be conducted every 8 weeks \pm 1 week regardless of study treatment delays through 24 months and then every 12 weeks \pm 1 week thereafter until confirmed disease progression per RECIST v1.1, initiation of a new anti-cancer treatment, withdrawal of consent, study termination by the Sponsor or death, whichever occurs first.

Tumour assessments must be performed independently of changes to the study treatment administration schedule (i.e. when treatment is withheld). If a tumour assessment has to be performed early or late, subsequent assessments should be conducted according to the original schedule based on the date of first study treatment administration.

Tumour assessments are to continue according to schedule in patients who discontinue treatment for reasons other than disease progression (unless subsequent anti-cancer therapy is initiated).

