Dermatologic examination [u]	x					x								x [u]		x [u]	x [u]
Ophthalmologic examination [v]	x					x								x [v]		x	
Intracranial disease assessment [w]	x									Last week of Cycle 2 then every 8 or 12 [w] weeks thereafter until PD							
Extracranial disease assessment [w]	x									Last week of Cycle 2 then every 8 or 12 [w] weeks thereafter until PD							

Appendix 2

Schedule of Activities for Cohort 2

Day	Screening [a]		Treatment Run-in (vemurafenib + cobimetinib)			Treatment (vemurafenib + cobimetinib + atezolizumab)								End of Treatment [b]	Long- Term Follow- Up [c]		
			Cycle 1			Cycle 2				Cycle 3				Cycle 4+			
	-28 to -1	-14 to -1	1	15	21	1	8	15	22	1	8	15	22	1	15	28 days after last study treatment	Every 3 months
Plasma for biomarkers [x]			x													At PD	
Concomitant medications [y]		x	x	x	x	x	x	x	x	x	x	x	x	x	x	x	
Adverse events [z]	x		x	x	x	x	x	x	x	x	x	x	x	x	x	Until 30 days after last study treatment	
Dispense vemurafenib [aa]			x		x	x				x				x			
Dispense cobimetinib			x			x				x				x			
Atezolizumab administration [bb]						x		x		x		x	x	x	x		
Study drug accountability [cc]				x	x	x	x	x	x	x	x	x	x	x	x		
Survival follow-up																x	

aPTT = activated partial thromboplastin time; ECOG = Eastern Cooperative Oncology Group; eCRF = electronic Case Report Form; INR= International Normalized Ratio; NA = not applicable; PD = progressive disease; RBR = Research Biosample Repository.

Appendix 2

Schedule of Activities for Cohort 2

Notes: All safety assessments (laboratory tests, ECGs, etc) should be performed within three days prior to Day 1. Unless otherwise specified, other assessments should be performed within seven days of the scheduled visit. On treatment days, all assessments should be performed prior to dosing, unless otherwise specified. If a protocol mandated study visit coincides with a holiday and/or weekend that preclude the visit, the visit should be scheduled on the nearest following feasible date.

- a. Results of standard-of-care tests or examinations performed prior to obtaining informed consent and within 28 days prior to initiation of study treatment may be used; such tests do not need to be repeated for screening.
- b. Patients who discontinue study treatment will return to the clinic for a Study Treatment Discontinuation Visit after 28 days (\pm 7 days) after their last dose of any study drug.

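### The Week-16 disease control window (Days 112–119) leaves out Days 105–111, when the protocol permits the scan, so some patients with stable disease or a confirmed response are scored as not controlled; read literally, an unconfirmed response in the window also scores worse than stable disease

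*SAP*

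**What the plan says.** SAP Section 5.4.2.6 places Week 16 at Study Day 112 and allows seven days after it but none before: "assessments that occur between Study Day 112 and Study Day 119 (inclusive) will be considered as a Week 16 assessment". A patient is controlled by meeting any one of three criteria:

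- **Bullet 1**, response in the window: "With a CR or PR assessed within the window of Study Days 112-119 inclusive and followed by a consecutive CR or PR assessment" at least 4 weeks later.
- **Bullet 2**, response before Day 112, where the next consecutive scan is also CR or PR, is at least 4 weeks later, and falls "weeks and on or after Study Day 112" (the 4-week spacing and the Day 112 condition both apply).
- **Bullet 3**, stable disease: "With a SD assessed within the window of Study Days 112-119 inclusive".

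On the denominator: "The denominator is all patients in the evaluable population". SAP Section 5.4 repeats the analysis in all treated patients, and Section 5.5.1.8 uses the same method for intracranial DCR by the independent review committee (IRC).

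The protocol defines DCR at 16 weeks without a window (Section 6.4.2). On scan timing, Section 4.5.6 says: "Intracranial and extracranial tumour assessments after end of Cycle 2 should be conducted every 8 weeks", with a tolerance of one week either way. After an early or late scan, "subsequent assessments should be conducted according to the original schedule based on the date of first study treatment administration". Footnote w of Appendix 2 repeats the 8-week rule for Cohort 2.

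**The concern.** The protocol's tolerance is two-sided and the SAP's window is one-sided. A scan on Days 105–111 is on schedule for the site but is not a Week-16 assessment for the analysis. Because the denominator is fixed, a patient who meets no bullet is not set aside as missing but is counted as a failure of disease control. Two patients with the same disease course can then be classified differently only because their scans fell on different permitted days.

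A second gap has a different cause. The bullets give no fallback for a CR or PR in the window that the next scan does not confirm, so a better scan result can score worse than SD.

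At stake are the intracranial, extracranial and overall DCR by investigator, in two populations, and the exploratory IRC version. With no hypothesis test in this study, these estimates and their intervals are the result for this endpoint.

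**Working it through.** **The SAP's own figure.** 16 × 7 = 112 and 112 + 7 = 119. The SAP window reproduces and contains 8 days.

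**Permitted days under the protocol.** Cycles are 28 days, so Cycle 2 ends on Day 2 × 28 = 56. Eight weeks later is 56 + 56 = Day 112. With ±7 days, the permitted range is Days 105–119, or 15 days. The SAP covers 8 of them and leaves out 15 − 8 = 7 (Days 105–111). If 16 weeks were counted as Day 113, the permitted range would be Days 106–120, and Days 106–111 and 120 would be left out, again 7 of 15.

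**The three bullets applied literally:**

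| Scan course | Result | Reason |
|---|---|---|
| SD 56, SD 108, SD 168 | Not controlled | No SD on Days 112–119 |
| SD 56, SD 112, PD 168 | Controlled | Bullet 3 |
| PR 56, PR 108, PD 168 | Not controlled | Confirming scan is before Day 112 |
| PR 56, PR 112, PD 168 | Controlled | Bullet 2 |
| SD 56, PR 108, PR 168 | Controlled | Bullet 2 |
| SD 56, PR 112, SD 168 | Not controlled | Unconfirmed PR; no bullet applies |

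In the first two rows, the patient with the longer documented control scores worse. Rows three and four differ only by a four-day shift in an on-schedule scan. Row five shows the limit of the problem: a response first seen on Days 105–111 and confirmed later is not lost. Likewise, SD on Days 105–111 still counts if a further SD scan falls on Days 112–119.

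**Size per patient.** 1/50 = 2.0 percentage points for the 50 planned evaluable patients in Cohort 2, and 1/60 = 1.7 for about 60 treated. The documents give neither the spread of scan dates nor the number of patients with SD. Assuming 1 to 5 affected patients, the loss is 2.0 to 10.0 points at n = 50 (5/50) or 1.7 to 8.3 points at n = 60 (5/60).

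**What widening the window would do by itself.** Take one scan on Day 56, one on each of Days 105–119 and one on Day 168, each CR/PR, SD, PD or missing. That gives 4 × 4 × 4 × 15 = 960 possible courses (counts, not frequencies). Using Days 105–119 in all bullets and treating an unconfirmed in-window response as SD makes 268 further courses controlled. Of these, 73 start with PD on Day 56, which leaves 268 − 73 = 195. The present bullets do not exclude earlier PD, and a wider window extends that gap. It would also credit SD on Day 106 followed by PD on Day 113. The fix must deal with both.

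**The case against.** The strongest defence is that the window is a deliberate landmark. The SAP openly allows time only after the exact Week 16, and bullet 2 independently asks for a scan on or after Day 112. On that view every bullet demands evidence at or beyond a full 16 weeks, and PR 56, PR 108, PD 168 fails as intended. This reading is coherent, but the SAP gives no such reason. It would not justify counting an on-schedule scan as a failure, and it does not explain why an unconfirmed PR on Day 112 scores below SD on Day 112.

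On that last point, the protocol requires responses to be confirmed for all endpoints, so an unconfirmed PR is properly not a response. That stands, but it does not make the scan SD. Protocol Appendix 5 defines SD as not meeting CR or PR, and the SAP supplies no bridge. This part depends on a literal reading, and one sentence settles it.

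Three stronger readings are tempting but not supported:

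- **Most sites miss the window even without using the tolerance.** A reader might infer this from the first-scan entry in Appendix 2, "Last week of Cycle 2 then every 8 or 12 [w] weeks thereafter until PD", by counting eight weeks from an actual scan on Days 50–56. Section 4.5.6 and footnote w count from the end of Cycle 2, and rescheduling is tied to first dose. Counting from the first scan would also make Days 99–119 permitted, which is not the documented schedule.
- **The SAP departs from the protocol without declaring it.** The protocol sets no DCR window, so the SAP is supplying an operational definition. Its absence from the SAP's list of changes to protocol-planned analyses is no fault.
- **A wider window is safe because no patient loses controlled status.** That follows from adding ways to qualify and says nothing about accuracy.

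**Conclusion.** The point holds as a defect in the DCR derivation. Seven of 15 permitted scan days are excluded, and the fixed denominator turns this into scored failures for two groups: patients with SD on Days 105–111 and no further SD scan on Days 112–119, and patients whose response is confirmed on Days 105–111 and followed by PD at the next scan. The unconfirmed in-window response is a separate gap. Each of these features can only lower DCR or leave it unchanged.

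The day counts follow from the documents. The 1-to-5-patient range is an assumption, and no overall bias is claimed: the lack of an earlier-PD exclusion works in the other direction. The working also assumes that the scan schedule in protocol Version 5.0 applies, although the SAP is written against Version 4.0.

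The consequence is limited to a descriptive secondary endpoint and its exploratory IRC counterpart. Nothing here bears on the primary intracranial ORR, PFS or OS. The rule should be settled before the DCR analysis, because a window chosen after results are known is hard to defend.

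**What to change.** In SAP Section 5.4.2.6:

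1. Define the Week-16 assessment as Study Days 105–119 in all three bullets, and replace Day 112 with Day 105 in both places in bullet 2.
2. Count a CR or PR in the window that is not confirmed as SD, for DCR only.
3. Where more than one scan falls in the window, use the last one. PD in the window then overrides an earlier SD or response, including one that would qualify under bullet 2.
4. Do not count a patient as controlled if RECIST v1.1 PD in that compartment was recorded before the Week-16 assessment.

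Apply these rules to the investigator DCR in both populations and to the IRC DCR in Section 5.5.1.8. Report the present Day 112–119 rule as a sensitivity analysis.

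The cost is SAP wording and one derivation, using scans already collected. SD may be credited up to one week before a full 16 weeks. Items 3 and 4 can also lower DCR: PD on Day 56 followed by SD on Day 112 counts as controlled today and would not under item 4. The sensitivity analysis will show the net effect.
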